1. To determine the feasibility of Mindfulness Based Stress Reduction (MBSR) for older cohabiting, intimate couples in which one, or both partners, has metabolic syndrome. We will (a) monitor recruitment, (b) adherence, and (c) missing data for the intervention. We will explore how being a couple impacts the MBSR experience, assessing (a) the prevalence of both partners having metabolic syndrome versus one partner, (b) shared decision making about participation and adherence, (c) how MBSR can be tailored to the needs of older couples, and (d) the impact on relationship quality and shared health behaviors.

2. To determine whether MBSR improves self-reported physical health status (SF-36) (Ware Jr & Sherbourne, 1992) for each partner. Hypothesis 1: The intervention group will have a significantly greater score on the SF-12 scale than does the control group.

3. To determine if MBSR reduces perceived stress (Perceived Stress Scale (Roberti, Harrington, & Storch, 2006)) and increases mindfulness (Kentucky Inventory of Mindfulness Skills (Baer, Smith, & Allen, 2004)). Hypothesis 2: Perceived stress will be reduced and mindfulness will increase for the MBSR group compared to the control group.

4. Exploratory aim: To determine if an MBSR intervention is associated with decreases in the composite measure of metabolic syndrome (blood pressure, waist circumference, glucose levels, cholesterol, triglycerides) for each partner. Hypothesis 3: The metabolic syndrome composite score for partners will be smaller at the end of the study in the MBSR group compared to the control group.

2. Background:

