Importantly, we will explore the dyadic effects of couple members' simultaneous engagement in the MBSR intervention. In addition to using proper statistical techniques to understand the effects of MBSR on each partner's outcomes, we will examine partner influences. For each primary hypothesis, we will examine the secondary hypothesis that each partner's improvement in each health outcome (self-report physical health, stress, mindfulness, and metabolic syndrome composite biomarker score) will be associated with improvement in the other partner's health outcome. In addition, we will examine the effects of the intervention on both partners' relationship satisfaction. Showing that relationship satisfaction can be enhanced is an important goal on its own, but we may also find that health outcomes improve when relationship quality improves.

3. Research Plan:

Procedures

Forty couples (N=80) will participate in a baseline visit to have blood drawn, BMI and BP measured, and to complete questionnaires assessing demographics, contextual factors, and baseline primary outcomes. Couples will be randomized to the MBSR condition (n=20 couples/ 40 individuals) or the wait list control condition (n=20 couples). The baseline blood draws and survey administration will take place at the CSRU, with the HRU as back up as needed. The blood analysis will be done by the YCCI Core lab. All participants will receive an informational sheet about metabolic syndrome.

Participants will be randomized to the intervention or wait-list group after informed consent is obtained, the initial blood is drawn and survey baseline is completed at the CSRU. A random digit generator will be used that assigns a condition (in this case, intervention or wait list) to each couple ID number.

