MBSR condition: MBSR is a standardized protocol consisting of 8-weekly 2.5 hour sessions, homework consisting of 30-45 minutes of mindfulness meditation practice six days per week and a one-time half-day (4-6 hour) retreat. This will be offered at the Social Gerontology and Health lab, [name] Our MBSR intervention is based upon the standard regimen taught at the University of Massachusetts.(Kabat-Zinn, 2013) Participants will attend weekly group sessions at the Yale Stress Center at the Yale School of Medicine taught by an experienced MBSR instructor ([name] MA MSW) who collaborates closely with Co-I [name]. Each weekly session will consist of an instructor-led mindfulness meditation, followed by a discussion of the meditation and its application into participants' everyday life. Formal meditations that will be led and discussed include eating meditation, body scan, sitting meditation, Hatha Yoga, and walking meditation. Participants will take their partners blood pressure reading with an automated Carescae cuff at each MSBR class. In addition, informal mindfulness practices of awareness of pleasant and unpleasant events and awareness of routine events will be discussed. Participants will be recording their daily mindfulness practice minutes on attached form.

Wait list condition: After the MBSR condition groups have completed their sessions, the participants in the Wait List group may choose to participate in the 8-week MBSR class. Participants will be provided with a coupon to participate starting July 2018. In the meantime, participants in the Wait list group will complete the same measures at the same time points as participants enrolled in Cohort 1 and Cohort 2 of the MBSR conditions.

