Accounting for simultaneous participation of couple members in MBSR for manual development. Prior to recruitment, the team will meet with [name], the MBSR instructor to adapt the MBSR manual so that it accounts for couples participating in the classes. Although the MBSR curriculum will not be substantially altered from its validated form, [name] will provide suggestions about how each practice and assignment in the program can acknowledge the partner's presence. We will maintain the standard MBSR program so that it can be easily disseminated to the public in later phases of this research. We are not developing a new relationship oriented MBSR. Rather, we will provide instruction about how each assignment should be carried out knowing that the partner is also in the program at the same time. Upon completion of the study, we will obtain interventionist feedback about how couple participation may have altered the MBSR program. [name] will keep notes about the influence of couple dynamics in her classes throughout the study and summarize them in a team meeting with the PI, Co-Is, and Project manager every 4 weeks and at the end of the study.

Measurement Schedule

	# of items	Variable type	Recruit	Baseline assess	8-week assess
Recruitment					
Referral or chart review: Potential participant has 3 of the following? (a) Abdominal obesity: waist circumference >102 cm in men, >88 cm in women; (b) Hypertriglyceridemia: ≥ 150 mg/dL (1.69 mmol/L); (c) Low high-density lipoprotein (HDL) cholesterol: <40 mg/dL (1.04 mmol/L) in men, <50 mg/dL (1.29 mmol/L) in women; (d) High blood pressure (BP): $\geq 130/85$ mm Hg and/or taking BP medication; (e) High fasting glucose: ≥ 110 mg/dL (≥ 6.1 mmol/L).	1	Inclusion criteria	X		
Participant is 60 or over.	1	Inclusion criteria	X		
Participant married or in romantic relationship?	1	Inclusion criteria	X		
Are they living together?	1	Inclusion criteria	X		
Participant's partner interested in being in the study?	1	Inclusion criteria	X		
Both partners age 60 or over?	1	Inclusion criteria	X		
Either partner non-English speaking?	1	Exclusion criteria	X		
Either partner practice mind-body therapies more than once/week (yoga, meditation)?	1	Exclusion criteria	X		
Either partner taking psychiatric medications?	1	Exclusion criteria	X		
Random assignment to intervention or waitlist control group	1	Intervention/control status			

Self-report Measures (Both partners)					
Socio demographics: age, gender, education, income	4	Covariates		X	X

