Physical health symptoms (SF-12)	12	Primary outcome		X	X
Perceived stress scale (Roberti et al., 2006)	10	Primary outcome		X	X
Kentucky Inventory of Mindfulness Skills (Baer et al., 2004)	39	Primary outcome		X	X
Relationship Assessment Scale (Hendrick, 1988)	7	Secondary outcome		X	X
Health behavior questionnaire (sleep, physical activity, eating behavior, medication adherence (Schulz et al., 1997))	22	Secondary outcome		X	X
Couples' decision making in participation and adherence: 1) How was your partner involved in your decision to first participate in the intervention? (Responses: a. encouraged you, b. discouraged you, c. neither) 2) How was your partner involved in your decision to continue with each class? (Responses: a. encouraged you, b. discouraged you, c. neither) 3) Open ended question: Describe how participating with your partner influenced your experience with the intervention.	3	Exploring couple dynamics			X
Biological Measures (Both partners)					
Blood draw: to assess hypertriglyceridemia and low high-density lipoprotein (HDL) cholesterol and high fasting glucose	3	Secondary outcome		X	X
Abdominal obesity- waist circumference per WHO protocol (2011)	1	Secondary outcome		X	X
Blood pressure (automated Carescape cuff)	1	Secondary outcome		X	X
Do both partners, only the husband, or only the wife have metabolic syndrome at baseline?	1	Exploring couple dynamics			
Feasibility Measures (Both partners)					
Percent of couples who screen versus enroll (Project manager keeps a record.)	1	Feasibility outcome	X		
# of MBSR sessions attended (Interventionist takes attendance.)	1	Feasibility outcome			X
Total minutes of home MBSR practice (Participants keep a daily record.)	1	Feasibility outcome			X

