The baseline, 8-week, and 3-month visits will entail data collection using validated questionnaires and self-report paper forms at the CSRU. The eight week visit will take place between five to eleven weeks after enrollment. The three month visit will occur from 10 to 14 weeks after enrollment. At the 8-week visit participants will be asked to complete a qualitative interview in addition to the paper surveys. Responses will be recorded on a cell phone and we will use transcription plus LLC <https://www.transcriptionplus.net> transcription services. Participants will complete the forms themselves, and they will be entered into the OnCore system by the project manager. These forms will be kept in paper form in each study participant's record and will be kept in a locked file cabinet at the Yale Center for Clinical Investigation. Only the PI and project manager will have access to the participant's records. Forms will be coded with subject number; no personally identifiable information will be associated with these forms. Blood will be drawn by staff at the Church Street Research Unit and sent to the YCCI Core Lab for processing of the glucose, cholesterol, and triglyceride markers. The biomarker information will then be linked to our study on OnCore. The OnCore database will be supported by the Yale Center for Clinical Investigation/ CTSA. Incomplete or missing data prompts follow-up calls or electronic queries in OnCore. Our OnCore database will be checked for completeness in real-time from internal checks; while the PI and project manager will perform weekly audits for complete data.

The project manager will use a study cell phone for the purposes of recruitment, and reminder texts for participants. The project manager will make routine follow-up calls to remind study subjects of their appointments. Attrition will be minimized and data collection optimized with a relatively short intervention duration together with a \$150 individual participant remuneration. Payment will be made through the ONCORE bank of America gift card program with remuneration to be as follows. (\$50 dollars at baseline, \$50 dollars at eight week follow-up and \$50 dollars at three month follow-up) In [name] ongoing studies in fibromyalgia and Irritable Bowel Syndrome patients (n=108), he has achieved complete (no missing data) datasets based on robust data collection, retention, and follow-up procedures in collaboration with the YCCI.

Timeline.

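### The question on partner involvement in the decision to join is asked only at 8 weeks, after randomisation, when it could be asked at baseline; the class-related items do not fit the wait-list arm

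*Protocol*

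**What the plan says.** Aim 1 (Protocol, Section I, item 1) undertakes to explore, among other couple-related matters, "shared decision making about participation and adherence". Aim 1 carries two lettered lists; this is entry (b) of the second.

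Three items in the Measurement Schedule serve that purpose. Item 1 asks "How was your partner involved in your decision to first participate in the intervention". Item 2 asks "How was your partner involved in your decision to continue with each class". Both offer three answers: encouraged, discouraged or neither. Item 3 is open-ended and asks how taking part alongside the partner shaped the experience of the intervention. The single X for the set is in the 8-week column; recruitment and baseline are blank. The schedule classes the items as exploring couple dynamics.

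On timing, Section I, item 3 (Procedures) states: "Participants will be randomized to the intervention or wait-list group after informed consent is obtained", and adds that the baseline blood draw and survey also come first. The Recruitment, Data management plan, and Retention paragraphs state: "The eight week visit will take place between five to eleven weeks after enrollment". For the control arm, the Wait list condition paragraph says that "participants in the Wait list group will complete the same measures at the same time points" as the MBSR cohorts, and that the class is open to them only once the MBSR groups have finished.

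**The concern.** Item 1 asks about a decision that is complete before anyone is randomised, but collects the answer weeks later. By then the participant knows the arm and, if assigned to MBSR, has attended classes with the partner whose influence is being rated. Both can colour recall. The answer is also available only from people who supply 8-week data. If discouraged people are less likely to do so, the recorded share of discouragement is too low.

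Item 2 is about continuing with classes, and item 3 is about the experience of the intervention. Neither has a sensible answer from someone who is still waiting for the course.

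At stake is what the pilot learns about a couple-specific barrier to feasibility. Under item 13 (Statistical Considerations), answers to the decision-making questions become coded attributes in the qualitative analysis. That analysis is then used to form hypotheses about the quantitative and dyadic results, so a distorted answer would carry into those hypotheses.

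**Working it through.** No stated sample size, power or alpha bears on this point, so there is no protocol figure to reproduce. The check compares the timing statements and then asks how far the size of the problem can be pinned down.

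**1. Order of events for item 1.** Decision to join, then consent, baseline blood draw and survey, then randomisation, then classes (MBSR arm), then item 1 at 5 to 11 weeks after enrolment. A baseline questionnaire already sits between the decision and randomisation, so item 1 could be asked there.

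**2. Timing of item 2.** The course has 8 weekly sessions (MBSR condition paragraph) and the visit window opens at week 5. One retrospective answer covers all classes, and for some participants it can be given before the last classes. No partner-influence item is scheduled for when someone stops attending.

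**3. Applicability by arm.** Each arm has 20 couples, or 40 people. Items 2 and 3 refer to a course that the wait-list arm has not attended by 8 weeks, so they do not apply to 40 of 80 participants. The protocol states no exemption.

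**4. Other planned sources.** "At the 8-week visit participants will be asked to complete a qualitative interview in addition to the paper surveys", so the interview reaches the same respondents. The instructor "will keep notes about the influence of couple dynamics in her classes throughout the study"; these notes run through the course but cover couples seen in class. For couples who do not enrol, the schedule keeps only a screened-versus-enrolled percentage. None of these replaces a pre-randomisation answer to item 1.

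**5. Possible size of under-recording (assumed inputs).** Let L be the number of the 80 without 8-week data, ps the share with a discouraging partner among responders, and pl that share among those lost.

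Unseen share of discouragement = L·pl / [L·pl + (80 − L)·ps]

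The protocol gives no separate dropout rate. Its Power paragraph reduces 80 to an effective 70 for loss to follow-up and couple dependency together (10/80 = 12.5%). L = 10 therefore uses the whole of that allowance for loss.

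| L | ps | pl | Calculation | Unseen share |
|---|---|---|---|---|
| 10 | 10% | 10% | 1/(1 + 7) | 12.5% |
| 10 | 10% | 30% | 3/(3 + 7) | 30% |
| 10 | 10% | 50% | 5/(5 + 7) | 42% |
| 10 | 5% | 50% | 5/(5 + 3.5) | 59% |
| 10 | 5% | 100% | 10/(10 + 3.5) | 74% |
| 5 | 10% | 50% | 2.5/(2.5 + 7.5) | 25% |
| 2 | 10% | 50% | 1/(1 + 7.8) | 11% |

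In the third row the true share is (5 + 7)/80 = 15% and the observed share is 10%. The observed share is too low whenever pl exceeds ps. With pl equal to ps, as in the first row, it is unbiased even though some cases are missed. By how much it is too low depends entirely on L, ps and pl, none of which the protocol supplies.

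**The case against.** A reader might infer that discouraging partners go largely unseen and that the aim is answered only by those who stayed with the course. The protocol does not support either statement.

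- **Missing the visit is not the same as stopping classes.** Nothing limits the 8-week visit to people still attending. It is paid ($50), participants receive reminder calls, and missing data prompt follow-up calls or queries. Someone who quit because of a partner can still say so.
- **A majority unseen needs strong assumptions.** For example, suppose half of discouraged participants miss the form against 10% of the others. A true 15% is then observed as 0.075/(0.075 + 0.765) = 8.9%. But that input itself sets the unseen share at half, and it implies 1 − 0.84 = 16% missing overall, more than the 12.5% combined allowance.
- **A baseline question does not reach couples kept out by a partner.** The partner's interest is an inclusion criterion, so those couples are absent at baseline too.
- **A larger usable sample for item 1 comes from rewording, not timing.** Asked about joining the study, the question could be answered by all 80 at 8 weeks as well.
- **The wait-list mismatch may be only loose drafting.** The schedule also lists sessions attended and home practice minutes, which plainly cannot apply to that arm before it takes the class.
- **The items are exploratory.** Attendance, practice minutes and the screened-versus-enrolled percentage measure feasibility independently of them.

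All of this stands as a limit on size and severity. It does not answer the timing point: item 1 is collected after randomisation although an earlier form is available, and the gain in recall and freedom from knowledge of the arm does come from moving it. The wait-list mismatch also remains to be clarified, since the protocol assigns that arm the same measures without exception.

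**Conclusion.** The point holds as a minor design weakness. Item 1 is asked only at 8 weeks, after randomisation and, in the MBSR arm, after exposure to classes. Its answers are open to recall and to knowledge of assignment, and they come only from people who give 8-week data. This much rests on the schedule and the stated order of procedures and needs no assumption. Items 2 and 3 do not fit the 40 wait-list participants at that time.

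Discouragement may be under-recorded. The direction depends on discouragement being more common among those without 8-week data, which is plausible but not shown. The amount cannot be estimated from the protocol: the 12.5% to 74% range with 10 lost reflects assumed inputs, so a claim that most discouragement is missed would go beyond the document. The primary comparison is unaffected.

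**What to change.** 1. Move item 1 to the baseline questionnaire, before randomisation, in both arms, worded about the *decision to take part in the study*.
2. State that items 2 and 3 are for the MBSR arm only. Ask item 2 of people who stopped attending as well, worded so that it covers stopping, and use the existing missing-data follow-up calls for those who miss the visit.
3. Add a reason code such as *partner not willing* to the screened-versus-enrolled record the project manager already keeps. This is the only one of the three changes that can capture couples who never enrol.

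The cost is a slightly longer baseline form, one extra question on some follow-up calls and one extra code in the screening record. No visit is added.

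### The 8-week visit may take place from week 5 after enrollment, although the eight weekly sessions cannot end before week 7, and its window overlaps the 3-month window at weeks 10 to 11

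*Protocol*

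**What the plan says.** The two follow-up windows are in the Protocol, Section I, item 3, under Recruitment, Data management plan, and Retention: "The eight week visit will take place between five to eleven weeks after enrollment", and "The three month visit will occur from 10 to 14 weeks after enrollment". Both are counted from enrollment.

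The intervention is described in the same item under MBSR condition: "MBSR is a standardized protocol consisting of 8-weekly 2.5 hour sessions", with "homework consisting of 30-45 minutes of mindfulness meditation practice six days per week" and one half-day retreat. Under Procedures, the order of events is fixed: "Participants will be randomized to the intervention or wait-list group after informed consent is obtained", and after the baseline blood draw and survey. Under Wait list condition, control participants "will complete the same measures at the same time points as participants enrolled in Cohort 1 and Cohort 2 of the MBSR conditions".

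The Measurement Schedule places the SF-12, perceived stress, mindfulness, blood draw, waist circumference and blood pressure at baseline and at the 8-week assessment. The items on the partner's part in deciding to join and to continue appear at the 8-week assessment only. The interview is also placed there: "At the 8-week visit participants will be asked to complete a qualitative interview in addition to the paper surveys". Item 13, Statistical Considerations, treats baseline, 8 weeks and 3 months as three separate assessment points in the dyadic repeated-measures model.

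**The concern.** The 8-week visit is the first measurement after the course and carries most of the follow-up data. Its window is a tolerance of 3 weeks either side of week 8, but the course leaves far less room on the early side. A visit that satisfies the Protocol can therefore fall while classes are still running.

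Only the MBSR arm has a course to cut short, so a mid-course assessment tends to shrink the 8-week difference between the arms. It also means that blood, waist, blood pressure and the interview may be collected before the exposure they are meant to follow. The Protocol's own rationale for Aim 4 is that biomarkers change once practice has become part of daily life, so an early draw works against that rationale.

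The overlap is a smaller, separate problem. One participant's 8-week visit may be later after enrollment than another's 3-month visit, and one participant's two visits may fall in the same week, although the model treats them as different points in time.

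**Working it through.** **Inputs** (all from Section I, item 3): 8-week window, weeks 5 to 11; 3-month window, weeks 10 to 14; 8 weekly sessions of 2.5 hours; home practice of 30 to 45 minutes on six days a week; no class before enrollment. The lag from enrollment to first class, k weeks, is not in the readable text (the Timeline table did not survive), so k = 0 is the base case and other values are assumptions.

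**The stated window.** 8 − 3 = 5 and 8 + 3 = 11, so the window is symmetric about week 8.

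**When the course ends.** Session i falls at week k + (i − 1), so session 8 falls at week k + 7. With k = 0 that is week 7. The margin before week 8 is 8 − 7 = 1 week; the tolerance allowed is 3 weeks; the excess is 2 weeks. If enrollment is read as the date of the first class, this is the same k = 0 case.

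**Exposure at an early visit, k = 0.**
- By week 5, sessions at weeks 0 to 5 have been held: 6 of 8 (75%), or 6 × 2.5 = 15 of 8 × 2.5 = 20 class hours. This is a maximum. If the visit precedes that week's class, it is 5 of 8. The retreat is left out because its date is not given.
- By week 6, at most 7 of 8 sessions.
- Home practice by week 5: 5 × 6 × 30 = 900 to 5 × 6 × 45 = 1350 minutes. Counting the 7 weeks between session 1 and session 8, the full amount is 7 × 6 × 30 = 1260 to 7 × 6 × 45 = 1890 minutes, so 5/7 = 71%. Counting 8 practice weeks instead gives 5/8 = 63%.

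**Share of the 8-week window that precedes session 8** = (k + 7 − 5)/6, up to a maximum of 1:

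| Lag k (weeks) | Session 8 at week | Share of window before session 8 |
|---|---|---|
| 0 | 7 | 2/6 = 33% |
| 1 (assumed) | 8 | 3/6 = 50% |
| 2 (assumed) | 9 | 4/6 = 67% |
| 4 (assumed) | 11 | 6/6 = 100% |

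These are shares of the window, not rates of early visits.

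**Overlap.** Weeks 5–11 and 10–14 share weeks 10–11, which is 1 week: 1/6 = 17% of the first window and 1/4 = 25% of the second. Taken in order, a participant's two visits may be 0 weeks apart (both in weeks 10–11) or as much as 14 − 5 = 9 weeks apart.

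**The 3-month visit.** With k = 0 it falls 10 − 7 = 3 to 14 − 7 = 7 weeks after session 8.

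**The case against.** The strongest reply is that the window is a tolerance around a visit named for week 8, not an instruction to assess at week 5. Staff may in practice have scheduled by cohort, the lost Timeline may have shown this, and the rule that wait-list participants are measured at the same time points fits that reading. Item 13 does not say which follow-up visit Hypothesis 1 uses, Hypothesis 3 refers to the end of the study, and questionnaires are collected again at 3 months. The trial is a pilot, and rules for assigning visits to time points commonly sit in an analysis plan, which is not at hand. The question about continuing with each class can be answered mid-course, so it is only weak evidence of what the visit is for.

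Much of this stands as a limit on the consequence. The rate of early visits is unknown, no dilution can be quantified, and nothing here raises the false-positive risk. Attendance and home-practice totals are not shown to be affected, since both are recorded throughout the course. The 3-month questionnaires recover part of what an early visit loses.

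It does not remove the mismatch. Even in the most favourable case, the stated window permits a visit that cannot be post-course. An analysis plan could settle how visits in weeks 10 to 11 are labelled, but no analysis rule turns a week-5 blood draw or interview into a post-course one. The readable text puts the interview and the couple items at the 8-week visit only, and does not clearly schedule biological measures at 3 months. For a pilot meant to supply effect sizes to later studies, partial-course measurements matter.

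**Conclusion.** The concern holds. As written, the Protocol allows its 8-week assessment two weeks before the earliest possible end of the course, after at most 6 of 8 sessions, and lets the two follow-up windows overlap by one week with no minimum gap. The week-7 figure rests only on weekly sessions and on no class preceding enrollment; any lag to the first class widens the mismatch. The direction of harm, dilution of the 8-week comparison, follows from the course existing in one arm only. Its size depends on how often early visits occur, which the Protocol does not show. This should be fixed: it is a clear conflict between the visit window and the intervention schedule. The overlap is the lesser part.

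**What to change.** Open the post-course window no earlier than the last session of the couple's cohort. Define the follow-up window from that same date, so that the two windows cannot overlap. Apply the same calendar dates to the wait-list couples of that cohort, as the existing rule on common time points already implies. Record the actual visit dates so that the repeated-measures analysis can use them.

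This changes Protocol wording and visit scheduling and adds no visits. The costs are that visits cluster in the weeks after each course ends, which loads the research unit, and that follow-up may move later. The new dates must be checked against the wait-list offer: "Participants will be provided with a coupon to participate starting July 2018". If follow-up ran past that date, control couples could begin the course before their last assessment. The readable text does not give the class dates needed for that check.
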